#### 9.6. DATA PRESENTATION FOR TOTAL IGG, IGG SUBCLASSES AND SPECIFIC IGG ANTIBODY LEVELS (PK TROUGH SET, SPECIFIC IGG TROUGH PK SET AND DENSE PK SUBSET)

#### 9.6.1. Listings and Summary Tables

The actual sampling time of blood sample collection for determination of serum concentrations of total IgG, IgG subclasses or antigen-specific IgG will be listed for each infusion schedule for all subjects, and will include the deviation from scheduled sampling time relative to sampling time window described in protocol and in the footnote to Table 1.

All individual serum IgG concentrations (g/L) will be listed by subject, time point and dosing interval (Q3/Q4W), together with body weight, and body weight adjusted dose and actual total dose for each infusion. Concentrations will be summarized for each nominal time point and specific analyte by infusion schedule, age category and dose range level for latest dose before sampling as described in Section 9.4.

Individual PK parameters will be listed for the Dense PK Subset (total IgG/IgG subclasses and antigen-specific IgGs) in a table by subject for each analyte (total IgG, IgG subclasses, antigen-specific IgG) and will be summarized, by infusion schedule, age category and dose level as described in Section 9.4. Unreliable PK parameters will be listed and flagged in the listing, but potentially excluded from the summary.

Pharmacokinetic parameters of secondary interest for all analytes – total IgG, IgG subclasses and specific IgGs, namely R-square adjusted, the number of data points used for estimating  $\lambda z$ , the upper and lower time point used for estimation of  $\lambda z$  (h) compared to t1/2z (h), and the % AUC extrapolation from tlast to infinity will be listed by subject with the resulting flags for the primary PK parameters.

The summaries will be calculated based on dose adjustment as described above in Section 9.4.

Key PK parameters derived from the "in silico" reduced data set will be listed separately and labeled "CFB" (change from baseline).

In addition, for the IgG subclasses, each individual concentration (g/L) will be transformed to the relative proportion of the total of the 4 subclasses (percent of the total). Individual percentages will be listed in same table reporting the concentrations (g/L) and summarized separately for the Q3W and Q4W regimen (all subjects and all doses together).

#### 9.6.2. Figures for Trough Total IgG Concentrations

The following mean trough concentration profiles will be produced for total IgG measured for all subjects, vs infusion number from 1st dose of BT595.

- Mean ± SD (all subjects, all doses together) of serum trough total IgG concentration at each infusion number will be presented vs infusion number/day of treatment combining curves for Q3W and Q4W dosing interval on the same plot together. Separate plots will be generated with the y-axis as (i) linear and (ii) logarithmic yaxis.
- 2. Mean ± SD (all subjects) serum trough total IgG concentration vs infusion number profiles for each dose range level (0.2-<0.4; 0.4-<0.6; and 0.6-0.8) will be presented combining the curves within the same figure, on linear y-axis scale separately for each infusion schedule. A second plot will be generated with logarithmic y-axis scale.
- 3. Mean ± SD serum trough total IgG concentration vs infusion number profiles will be presented for each age category separately for each dosing interval. Separate plots will be generated with the y-axis using a (i) linear and (ii) logarithmic scale.
- 4. Individual profile of serum trough total IgG concentration vs infusion number will be presented on the same plot, separately for each dosing interval (Q3W / Q4W) and age category. Subjects with changes to the dose levels will be identified in the footnotes to the figures including time of dose adjustment and level of adjusted dose. Separate plots will be generated with the y-axis as (i) linear and (ii) logarithmic y-axis.
- 5. Figures 1.-3. (Mean ± SD) and Figure 4. (individual) will additionally be generated with the x-axis being actual time relative to the start of the first infusion (= time 0) with time in days or weeks as appropriate. Separate plots will be generated with the y-axis as (i) linear and (ii) logarithmic y-axis.

Figures presenting data for the different age categories will be produced for FDA and EMA categories separately. The number of subjects in each age category will be given in the legend. A horizontal reference line of the targeted minimal trough level of 5 g/L will be displayed in all figures as dotted line.

#### 9.6.3. Figures for Baseline and Steady State Trough Levels

Steady state trough concentrations will be measured for all subjects for total IgG, and predefined age categories for the IgG subclasses (6 to <76 years) and antigen-specific IgG (12 to<76 years). Total IgG and IgG subclasses trough concentrations for baseline and predose for 7th/5th infusion (Q3W / Q4W) will be available from (Total IgG) and central (IgG subclasses) lab for all subjects in all age categories. Trough concentrations obtained as a

part of Dense PK sampling will not be included in the figures. All antigen-specific IgG trough concentrations for the Specific IgG Trough PK Set will be only available from central lab (Biotest).

Data will be presented by Box-whisker plots for the 2 time points. A first set of figures will present baseline (which is the trough concentration of a similar product used by subjects previously to the study) and steady state data for all subjects together, and Q3W and Q4W separately on the same graph (6 boxes). Separate figures will be provided for each of the IgG variable (total IgG, 4 subclasses, and 6 antigen-specific IgGs).

A similar set of figures will present baseline and steady state levels for each age categories (FDA, EMEA categories on separate graphs) for each dosing interval and for each IgG variables on separate figures (total IgG, 4 subclasses, and 6 antigen-specific IgG).

Additionally, figures for different age categories will be produced for dose-normalized steady-state concentration  $C_{ss}/D$  for total IgG, IgG subclasses, and specific IgGs after the 7th BT595 infusion for Q3W schedule or the 5th infusion for Q4W schedule by age category on the same box plot.

Finally, a figure representing only the steady state concentrations of total IgG measured once in local lab and once in central lab for the subjects participating to the PK dense sampling will be presented by Box-whisker plots for the 2 measurement methods, see Section 9.4.3 (Multiple PK set).

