6.2.1 Dose Changes during the Study

The subject's total IgG trough levels from the previous infusion will be assessed at the local laboratory to allow dose adjustment at the next infusion if a subject's trough level was below 5 g/L. Serum trough levels of IgG \geq 5 g/L must be met throughout the study. If a subject's IgG level changes to <5 g/L, the subject's dose must be adjusted to meet the target trough levels. Dose changes will be made at the investigator's discretion and must follow the dosage regimen detailed in Section 6.2 (i.e., 0.2 to 0.8 g/kg bw [2 to 8 mL/kg] administered as intravenous infusions at 3- or 4-week intervals).

Body weight will be assessed before each study infusion in order to calculate an accurate dose for each subject's dose infusion. The investigator will calculate the percentage change in the subject's body weight since the last assessment. If a subject's body weight changes by <5% from the weight used for the current dose, the total dose will remain the same as the current dose. If a subject's body weight changes by $\geq 5\%$ from the weight used for the current dose by $\geq 5\%$ from the weight used for the current dose (g), but not the dose per weight (g/kg), will be adjusted accordingly to maintain a constant dose in g/kg/infusion during the study.

Any changes in dose and the reason for the change in dose will be recorded in the eCRF.

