#### 5.5. PK TROUGH SET

The PK Trough Set includes all subjects following the principles of the SAF for whom at least 1 trough concentration of total IgG in the age group 2 to <76 years and/or subclass IgG in the age group 6 to <76 years (measured in local laboratory) is available. All PK analyses involving trough concentrations will be conducted using the PK Trough Set.

The total IgG PK concentrations measured at the end of 1st infusion by local labs will be also presented for the PK Trough Set, but not used for the calculation of summary statistics of the trough concentration of total IgG.

Additional trough samples for the 5th/7th infusion measured centrally via separate analytical method for the dense PK characterization and used for the Dense PK Subset data will not be included in the PK trough set.

Upon review, complete profiles or only certain time points may be excluded from the summary of trough concentrations from subjects who did not receive proper study medication dosing or had out-of-window sampling.

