#### 9.4.3. Steady State Trough Concentrations (Multiple PK Sets)

For comparison purpose, steady state trough concentrations ( $C_{ss}$ ), defined as the trough concentration prior to infusion 7 for Q3W schedule and infusion 5 for Q4W, and measured both at local lab and at central lab (Biotest), will be listed for each subject. The steady state trough concentrations will be summarized separately for PK Trough set (local lab) for all subjects and for the Dense PK Subset (central lab) only for subjects participating to steady state PK study combined by age and dosing regimen (Q3W or Q4W). The comparison between local lab and central lab measurements will be done graphically for the subjects in Dense PK Subset as described in Section 9.6.3.

Antigen-specific IgGs will be summarized in a separate table for Specific IgG Trough PK Set.

In addition, steady-state trough concentrations Css of total IgG normalized by dose level i.e. divided by actual administered dose will also be calculated. Latest dose level before measurement will be used for dose normalization.

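### The only planned comparison of local and central total IgG troughs is one box per laboratory method, which discards the within-subject pairing and gives no measure of agreement

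*SAP*

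**What the plan says.** SAP 9.4.3 covers the steady-state trough, taken before infusion 7 on the 3-week schedule and infusion 5 on the 4-week schedule. It states that the listing is there to support a comparison: values "measured both at local lab and at central lab (Biotest), will be listed for each subject". It then gives the method: "The comparison between local lab and central lab measurements will be done graphically for the subjects in Dense PK Subset", and refers to 9.6.3 for the graphic.

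SAP 9.6.3 describes that graphic for total IgG, "measured once in local lab and once in central lab", in the subjects with dense sampling. The values "will be presented by Box-whisker plots for the 2 measurement methods".

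The numerical summaries in 9.4.3 are "summarized separately for PK Trough set (local lab) for all subjects and for the Dense PK Subset (central lab"), so they rest on different sets of subjects.

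Two further passages give the context:
- SAP 5.5 says the additional troughs are "measured centrally via separate analytical method for the dense PK characterization", and keeps them out of the PK Trough Set.
- Protocol 6.2.1 says the total IgG trough "will be assessed at the local laboratory to allow dose adjustment at the next infusion if a subject's trough level was below 5 g/L".

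**The concern.** The two values come from one subject at one time point. They may come from separate tubes, but they remain paired by subject and infusion. Agreement between methods is a question about within-subject differences. One box per method shows mainly between-subject spread, which says nothing about agreement, and it breaks the link between the two values of a pair.

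Total IgG is reported on both scales. Local values feed the dose rule, the trough endpoint and the proportion below 5 g/L (SAP 8.2.1). Central values feed the dense PK parameters (SAP 5.7 and 9.5.1). SAP 5.5 itself says that the central method is a separate one. A reader of the study report who wants to know how far the two scales agree will find a listing and two boxes, with no estimate of the difference and no statement of its precision.

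**Working it through.** **No stated figure to reproduce.** The documents give no sample size, SD, assay error or acceptable difference for this comparison. The number of pairs is at least 20 adults plus consenting pediatric subjects aged 6 and over (SAP 3.5). All other inputs below are assumptions.

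**Assumptions.** Mean trough 8.5 g/L; between-subject SD (sB) 1.5 or 2.5 g/L; SD of the local-minus-central difference (sW) 0.3 or 0.6 g/L; constant bias 0.5 or 1.0 g/L; n = 20, 40 or 60 pairs; 4,000 simulated data sets per setting.

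**Precision at n = 20.**
- Paired: half-width = t(0.975; 19) × sW / √20. With t = 2.093 this is 2.093 × 0.3 / 4.472 = 0.14 g/L, and 2.093 × 0.6 / 4.472 = 0.28 g/L.
- Boxes read as independent groups: half-width = t(0.975; 38) × √[2(sB² + sW²/2)/20]. With t = 2.024 the ends of the range are 2.024 × √[2(2.25 + 0.045)/20] = 0.97 g/L and 2.024 × √[2(6.25 + 0.18)/20] = 1.62 g/L. The simulated averages are 0.95 to 1.60 g/L, slightly lower because a sample SD is on average a little below the true SD.
- At n = 60 the simulated ranges are 0.08 to 0.15 g/L paired and 0.54 to 0.92 g/L unpaired.

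**What a constant bias does to the boxes.** The box height is about 1.349 × √(sB² + sW²/2), which runs from 2.04 to 3.42 g/L. A 0.5 g/L bias moves the box by 15% to 24% of its height, and a 1.0 g/L bias by 29% to 49%. The median shift averages the bias itself, and the medians fall in the right order in 95% to 100% of simulated data sets. With noisier pairs (SD 2 g/L, bias 0.5 g/L, within-pair correlation 0.5 to 0.95) the right order appears in about 79% to 95% of data sets at n = 20 and 87% to 99% at n = 40. So the shift shows, but it is small against the spread and carries no precision.

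**What the boxes conceal.** Suppose half the local laboratories read 10% high and half 10% low. At a trough of 8.5 g/L that is 0.10 × 8.5 = 0.85 g/L in each direction. With 40 pairs and sB = 2.5 g/L, the medians differ by less than 0.1 g/L on average and the box heights by less than 10%, so the boxes look much alike. Even so, roughly 3% of pairs fall on opposite sides of 5 g/L. At sB = 1.5 g/L the local box widens more, by up to about 20%. A plot of within-subject ratios would show two clusters, near 1.1 and 0.9.

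**Separate summaries.** Local values are summarized for all subjects and central values only for dense-PK subjects. A difference between the two summary means therefore mixes a laboratory difference with a difference in who was measured.

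**The case against.** Much of the opposing case stands.

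- *The figure does show a systematic shift.* A reader might infer that the plot would hide any laboratory bias, or could not detect one. The documents do not support that: both boxes hold the same subjects, so a constant bias moves the whole box.
- *The pairs are reported.* Both values are listed per subject, so a reader can form the differences. Table and figure shells are in a separate document (SAP 6.1) that is not available here, so a difference column cannot be ruled out. But a listing is not an analysis, and the SAP text commits to none.
- *No test is planned.* It is tempting to quantify the loss as the power of a two-sample test against a paired one. The SAP plans no such test, and the usual two-sample power formula assumes independent samples, which these are not. The half-widths above show only what pairing adds to precision.
- *Dosing is unaffected.* A reader might link the figure to the 5 g/L dose rule. Central samples are stored until the end of the study and then measured (Protocol 9.5.2), and the pairs exist at one infusion only. The comparison is retrospective and could not recalibrate other visits.
- *Detail by laboratory will be thin.* With about 2 to 3 subjects per site (SAP 3.4), laboratory-specific bias is barely estimable, and the number of distinct local laboratories is not stated. Under SD 2 g/L, mean 8.5 g/L and bias 0.5 g/L, only about 0.4 to 2 pairs among 20 to 40 would fall on opposite sides of 5 g/L.
- *The SAP keeps the two scales apart.* For total IgG, the comparison with the former product uses the PK Trough Set at both time points (SAP 9.7), so a stable proportional local bias cancels in the ratio. The SAP never gives the box plot a formal validation role.

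**Conclusion.** The concern holds in limited form. The SAP sets out to compare two methods in the same subjects at the same infusion, and the only comparative display it specifies discards the pairing. A constant bias would be visible as a shifted box but without a precision. Subject-level scatter, concentration-dependent bias and opposite biases between local laboratories would be concealed, and the separate summaries cannot recover them.

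With 20 pairs and the assumed SDs, pairing narrows the 95% CI half-width for the mean difference from about 0.95–1.60 g/L to about 0.14–0.28 g/L. These figures depend on assumed variances. Whether a given bias would matter at 5 g/L cannot be settled from the documents, which give no acceptable difference.

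Severity is minor. This is supporting PK description, with no effect on dosing or on the primary infection-rate test.

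**What to change.** In SAP 9.4.3 and 9.6.3, add to the two-box figure, or put in its place, a plot of each subject's local/central ratio (or local-minus-central difference) against the pair mean. Report the mean ratio or difference with its 95% CI and the limits of agreement, computed in the Dense PK subjects who have both values.

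Optionally, mark each point by local laboratory and count the pairs that fall on opposite sides of 5 g/L. Label both as description only, given the small numbers.

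The cost is SAP wording and one figure. Both values are already collected and listed, so no new samples, visits or data are needed, and the dose rule is not touched.

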#### 9.6.4. Figures for Dense PK Sampling

PK profiles of total IgG, IgG subclasses, and antigen-specific IgG will be presented using data for all subjects participating to the dense PK sampling at steady state (at least 20 adults and voluntary pediatric patients) in the same way, on different plots unless otherwise indicated. The concentration data will be presented as original values and as change from baseline. The X-axis will indicate the time since last infusion (5th/7th infusion) in days. For the mean plots the nominal time will be used. All graphs will be provided with the y-axis as linear scale and as log-linear scale. Groups corresponding to infusion intervals, and age categories will be presented. Mean concentrations will be presented for all dose levels combined, without binning into separate dose ranges.

- Mean ± SD (all subjects, all doses together) of concentration at each nominal time point elapsed from the current infusion will be presented combining curves for the Q3W and Q4W schedules within the same figure on a linear and log-linear scale for total IgG, IgG subclasses, and antigen-specific IgG on separate plots.
- Mean ± SD (all doses together) concentrations at each nominal time point elapsed from the current infusion will be presented within the same figure on a linear and loglinear scale combining curves for each age category, separately for the Q3W and Q4W schedules. The plots will be produced for the FDA and EMEA defined categories.

1004675

Individual serum concentration-time profiles will be presented separately for each subject combining all analytes - total IgG, 4 IgG subclasses and 6 antigen-specific IgG on a linear and log-linear scale. The values of specific IgGs will be presented using Y2 scale to accommodate the use of different units – U/mL for specific IgGs vs g/L for all other IgG analytes.

In addition, overlay graphs of individual concentration-time profiles will be provided, separately for each dosing interval and each IgG variable (total, subclasses, antigen-specific) on linear and log-linear scale for each age category separately. The plots will be produced for the FDA and EMEA defined categories.

#### 9.6.5. Figures for PK Parameters

PK parameters will be presented on box plots for total IgG, 4 IgG subclasses, and 6 different antigen-specific IgG for each PK parameter individually ( $C_{max}/D$ , AUCtau/D and AUC0-inf/D, and t1/2z). Data will be reported separately for each dosing interval (Q3W and Q4W) and age category (FDA and EMA separately).

Box plots comparing PK parameters ( $C_{max}$ ,  $T_{max}$ , AUCtau, AUC0-inf,  $t_{1/2z}$ ) from complete and "in silico" reduced data sets will be presented by dosing schedule pooling together all subjects (6-75 years) and all dose levels.

#### 9.7. EXPLORATORY COMPARISON OF STEADY-STATE TROUGH CONCENTRATIONS FOR TOTAL IGG, IGG SUBCLASSES, AND SPECIFIC IGGS WITH PREVIOUS IGG FORMULATION

Exploratory comparison of  $C_{ss}$  and dose-normalized  $C_{ss}/D$  between BT595 and similar products (IVIG products) will be performed for age categories and overall by ANOVA. The data for PK Trough Set and Specific IgG Trough PK Set will be used.

Log-transformed parameters Css/D for total IgG, IgG subclasses and specific IgGswill be compared separately by dosing interval and by age category where possible with treatment as fixed effect and subject as random effect based on existing guidance on bioequivalence from EMA (European Medicines Agency Questions and Answers: positions on specific questions addressed to Pharmacokinetics and FDA (Food and Drug Administration (FDA) Guidance for Industry). The following hypotheses will be tested for Css values:

Ho1:  $\mu_T/\mu_R \le 80\%$  vs. Ha1:  $\mu_T/\mu_R > 80\%$  and Ho2:  $\mu_T/\mu_R \ge 125\%$  vs. Ha2:  $\mu_T/\mu_R < 125\%$ 

The same model will also be repeated for dose normalized trough concentration.

If the 90% CI for the geometric mean ratio (GMR) is within (80% - 125%) for any of the contrasts for the parameters Css/D, the null hypotheses, that is H01 and H02, will be rejected with conclusion that the administration with BT595 (T=Test) is equivalent to administration of the previous IgG formulation (R=Reference).

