A similar analytical approach might not be possible for pediatric subjects (2-5 years, inclusive) where only sparse sampling (total IgG only) is planned. Therefore, a population modelling approach will be proposed. First, a preliminary model based on prior PK data obtained with BT595 in adult subjects (18-75 years, inclusive) and pediatric subjects (6-17 years, inclusive) will be established. This model will be updated and used to reconstruct dense individual concentration-time profiles for all subjects, including the youngest pediatric subjects (2-5 years, inclusive), and to derive the different key PK parameters.

Finally, all data will be summarized by descriptive statistics for the study population as a whole, and for each age category. Data from the different age categories will be compared descriptively. However, no formal statistical analysis will be performed.

Evaluation of the total IgG trough levels will include the calculation of the proportion of subjects who failed to meet the target level (\geq 5 g/L) prior to dose adjustment. In addition, an intra-individual comparison to currently licensed IVIg products in the same subjects (i.e., using prestudy data) will be performed by suitable methods. No formal statistical test will be performed for these variables.

Pharmacokinetic data (including total IgG trough levels) will also be compared to historical data from previous PID studies with Intratect and Bivigam (already marketed 10% IVIgs) and to available data from literature.

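### SAP 9.7 draws a general equivalence conclusion from contrast-level results, which the protocol did not plan and SAP Section 13 does not list

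*SAP*

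**What the plan says.** SAP 9.7 is headed exploratory. It compares Css and Css/D on BT595 with the baseline trough on the prior IVIg by ANOVA on the log scale, separately by dosing interval and, where possible, by age category.

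The section then turns to formal testing. "The following hypotheses will be tested for" Css values, it says, and it gives two one-sided nulls at 80% and 125%. The model is to be repeated for the dose-normalised trough. The decision sentence requires the 90% CI of the geometric mean ratio to lie within 80% to 125% "for any of the contrasts for the parameters" Css/D. If so, the nulls "will be rejected with conclusion that the administration with BT595 (T=Test) is equivalent to administration of the previous IgG formulation".

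The contrast list that follows covers total IgG and subclasses 1-4 only: infusion 7 against baseline for the 3-week schedule, and infusion 5 against baseline for the 4-week schedule.

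Protocol 10.10 plans the intra-individual comparison with the prior IVIg, from prestudy data, in its paragraph on total IgG troughs. That paragraph states: "No formal statistical test will be performed for these variables". The synopsis repeats the sentence. SAP 9.4.1 refers the same total IgG comparison to Section 9.7.

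**The concern.** The condition is met contrast by contrast, but the conclusion is one statement about the product. As written, a single subclass on a single schedule could support a sentence in a pivotal study's report that BT595 is equivalent to what patients received before. No multiplicity control is stated for these contrasts, and neither document gives a power or variance basis for the comparison; the sample size rests on the serious bacterial infection rate alone.

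The reference is also not one product. Inclusion criterion (e) requires a single IVIg preparation within a subject but does not require the same one across subjects. A general claim of equivalence to the previous formulation therefore has no single comparator.

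Finally, a reader who checks SAP Section 13 for departures from the protocol will not find this one, although smaller changes, such as added annual rates, are recorded there.

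**Working it through.** **Inputs**
- Limits 80% and 125%, and a 90% CI: SAP 9.7.
- CI form (1 - 2α) × 100%: SAP 9.7. No numeric α is given.
- Listed analytes: total IgG plus four subclasses = 5. Schedules: 2. Source: the contrast list in SAP 9.7.
- Correlations between contrasts: in neither document, so assumed and shown as a range.

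**1. The plan's own figure.** Setting (1 - 2α) = 0.90 gives α = (1 - 0.90)/2 = 0.05 for each one-sided test. The 90% CI is thus consistent with two one-sided tests at 5%, and a single contrast has a false-equivalence probability of at most 5%.

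**2. Number of listed contrasts.** 5 analytes × 2 schedules = 10, before any age split.

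**3. If *any* means at least one.** Put every true ratio on a limit, with intervals narrow enough that the other limit does not matter, so each contrast passes with probability 0.05.
- All ten independent: 1 - 0.95^10 = 0.401.
- Perfect correlation within each schedule, with its ratios on the same limit, and independence between schedules: 1 - 0.95^2 = 0.0975. The schedules involve different subjects, so this is the lower end.
- Intermediate within-schedule correlations, from a simulation of 200,000 runs with independent schedules:

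| Assumed within-schedule correlation | P(at least one of 10 passes) |
|---|---|
| 0 | 40.1% |
| 0.5 | 30.7% |
| 0.8 | 21.8% |
| 0.95 | 15.4% |
| 1 (by formula) | 9.75% |

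The heading and text of 9.7 also include specific IgGs, although its contrast list does not. SAP 9.6.3 counts six of them, giving 11 analytes × 2 schedules = 22 contrasts and, if all are independent, 1 - 0.95^22 = 0.676. Age splits would add further contrasts, in a number the SAP does not fix.

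**4. If *any* means whichever contrast is being tested.** Each test keeps its 5% level and step 3 does not apply. The conclusion still names the product as a whole, so it goes beyond the result that triggers it.

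**5. Protocol against SAP.**

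| Analyte | Protocol | SAP 9.7 | SAP Section 13 |
|---|---|---|---|
| Total IgG | Comparison planned; formal test excluded | Hypotheses, rejection rule, equivalence conclusion | Not listed |
| Subclasses, specific IgGs | No such test planned | Same approach added | Not listed |

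**6. Parameter.** The hypotheses are written for Css and the model is repeated for Css/D. The decision sentence and the contrast list name only Css/D, so the SAP does not say how a Css result would be decided.

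**The case against.** The strongest reply is that the section is exploratory, that its hypotheses are defined on a single ratio with no global null, and that parameters are compared separately by dosing interval and age. On that view the decision sentence is meant contrast by contrast, and the 40% figure does not describe it. This reading is possible and the text does not exclude it. The analysis also feeds neither the primary endpoint nor the sample size, and nothing in the documents demands multiplicity control for exploratory PK contrasts. These points stand. They limit the consequence but do not confine the equivalence statement to the contrast that passed.

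A reader might also infer more than the documents support:
- *That the protocol bars formal testing for every analyte.* Its sentence closes a paragraph on total IgG troughs. The direct contradiction therefore covers 2 of the 10 listed contrasts; the other 8 are an addition.
- *That Css/D was left out of the modelling.* It was not. Only the decision sentence is narrower than the hypotheses.
- *That the before/after comparison is itself the defect.* The protocol plans an intra-individual comparison by suitable methods. The defect is the formal conclusion attached to it.

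**Conclusion.** The point holds as a wording defect with a real consequence. SAP 9.7 permits a product-level equivalence conclusion that the underlying contrasts do not support under either reading of the rule. For total IgG it contradicts the protocol, and Section 13 is silent on the change for all analytes.

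Under the at-least-one reading, the chance of a false conclusion over the 10 listed contrasts is about 10% to 40%, against at most 5% for one contrast. That range assumes every true ratio on a limit and narrow intervals. With wide intervals two one-sided tests reject less often, and the documents give no variance from which to judge this. The 40% end also needs full independence, which is implausible for total IgG and its subclasses measured in the same subjects. Neither figure should be quoted as the error rate of the plan, because the per-contrast reading remains open. The primary efficacy conclusion is not affected.

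**What to change.** Preferred: keep the models, report the geometric mean ratio and 90% CI for each contrast descriptively, and delete the sentence that rejects the nulls and concludes equivalence. For total IgG this restores agreement with the protocol.

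If a decision rule is kept:
- replace *any of the contrasts* with *a given contrast*;
- limit the statement to that contrast's analyte, schedule and age group;
- say whether Css or Css/D decides;
- list the added test in SAP Section 13 as a change from the protocol, separating total IgG (contradicted) from subclasses and specific IgGs (added).

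The cost is SAP wording only; no new data or models are needed. The downside is that the analysis yields no general equivalence statement, which the protocol did not plan.
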